### 7.4.4.2. Duration of Response by mRECIST v1.1

Under mRECIST v1.1, for objective responders, DOR is the time from the first overall response contributing to an objective response (CR or PR) to the earlier of the subject's death from any cause or first confirmed assessment of PD. Note that the criteria for the assessment of PD in DOR are the same with ORR, which are presented in Section 7.4.2.2.

#### 7.4.5. Duration of Disease Control

Duration of disease control (CR, PR, and SD) is defined as the time from the first report of SD or better until disease progression or death from any cause, if occurring sooner than progression, as determined by investigator assessment of radiographic disease per RECIST v1.1 and

mRECIST v1.1. Note that the criteria for the assessment of PD in duration of disease control are the same with ORR, which are presented in Section 7.4.2.2.

The duration of disease control will be estimated with 95% CIs overall and by treatment group. Confidence intervals will be calculated based on the exact method for binomial distributions. Swim plots for duration of disease control will be generated separately for RECIST v1.1 and mRECIST v1.1 criteria.

Subjects who do not have sufficient baseline or on-study response assessment information to be adequately assessed for response status will be included in the denominators in the calculation of rate of disease control.

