1.3.4. Rationale for the Study Endpoints

1.3.4.1. Efficacy Endpoints

Efficacy endpoints of this study are secondary and include objective response rate, duration of response, rate of disease control, and progression-free survival (PFS) by investigator assessment based on RECIST v1.1 and modified RECIST (mRECIST; a modified version of RECIST v1.1).

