2.2.2. Secondary Endpoints

- The PK of INCAGN01876 including C_{max} , t_{max} , C_{min} , and AUC_{0-t} for subjects in Parts 1 and 2 will be summarized.
- Objective response rate, defined as the percentage of subjects having complete response (CR) or partial response (PR), will be determined by investigator assessment of radiographic disease assessments per RECIST v1.1 and mRECIST v1.1.
- Duration of response, defined as the time from earliest date of disease response (CR or PR) until earliest date of disease progression, will be determined by investigator assessment of radiographic disease assessments per RECIST v1.1 and mRECIST v1.1, or death due to any cause if occurring sooner than progression.
- Duration of disease control (CR, PR, and stable disease [SD]), as measured from first report of SD or better until disease progression, will be determined by investigator assessment of radiographic disease assessments per RECIST v1.1 and mRECIST v1.1, or death due to any cause, if occurring sooner than progression.
- Progression-free survival, defined as the time from date of first dose of study drug until the earliest date of disease progression, will be determined by investigator assessment of objective radiographic disease assessments per RECIST v1.1 and mRECIST v1.1, or death due to any cause if occurring sooner than progression.

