9.4.1.2. Secondary Efficacy Analyses

The PK of INCAGN01876 will be summarized.

Duration of disease control, defined as the proportion of subjects who have disease control (CR + PR + SD), as per RECIST v1.1 and mRECIST v1.1 until the earliest date of disease progression will be summarized.

Progression-free survival and duration of response will be estimated using the Kaplan-Meier method as per RECIST v1.1 and mRECIST v1.1.

[REDACTED]

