### 2.2.2. Secondary Objectives

- To evaluate the PK of INCAGN01876 in subjects with advanced or metastatic solid tumors.
- To evaluate the preliminary efficacy of INCAGN01876 by assessing ORR, DOR, and rate of disease control per RECIST v1.1 and modified RECIST v1.1 (further referred to as mRECIST v1.1).
- To evaluate the preliminary efficacy of INCAGN01876 by assessing PFS per RECIST v1.1 and mRECIST v1.1.

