#### 7.1. General Considerations

Efficacy endpoints of this study are secondary and include ORR, DOR, duration of disease control, and PFS by investigator assessment based on RECIST v1.1 and mRECIST v1.1.

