### 7.4.4. **Duration of Response**

Duration of response will be assessed with RECIST v1.1 and mRECIST v1.1 criteria.

Censoring of DOR will follow the same algorithm as the censoring of PFS. Kaplan-Meier curves for DOR will be presented by cohort-specific tumor types. The KM estimate of median DOR will be presented with its 95% CI. The 95% CI will be calculated using Brookmeyer and Crowley's method (Brookmeyer and Crowley 1982). A swim plot for DOR will be generated under both RECIST v1.1 and mRECIST v1.1 criteria.

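### Rate and duration of disease control are conflated: a time-to-event endpoint gets an exact binomial interval with no estimator or censoring rule, and the rate has no definition or table row of its own

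*SAP*

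**What the plan says.** **Defined as a time.** Protocol 2.2.2 lists "Duration of disease control (CR, PR, and stable disease [SD]), as measured from first report of SD or better until disease progression", with death counting if it comes first. SAP 2.3.2 and the opening of SAP 7.4.5 say the same.

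**Analyzed as a proportion.** SAP 7.4.5 goes on: "The duration of disease control will be estimated with 95% CIs overall and by treatment group", and then "Confidence intervals will be calculated based on the exact method for binomial distributions". Its last paragraph gives a denominator rule, but for the rate of disease control.

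**Defined as a proportion.** Protocol 9.4.1.2 reads: "Duration of disease control, defined as the proportion of subjects who have disease control".

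**Rate and duration change places.** The secondary objective in SAP 2.2.2 speaks of "assessing ORR, DOR, and rate of disease control per RECIST v1.1", and Protocol 2.1.2 agrees. Protocol 1.3.4.1 says that the efficacy endpoints "include objective response rate, duration of response, rate of disease control, and progression-free survival (PFS) by investigator assessment". The matching sentence in SAP 7.1 is "Efficacy endpoints of this study are secondary and include ORR, DOR, duration of disease control, and PFS". The endpoint lists (Protocol 2.2.2, SAP 2.3.2) contain only the duration.

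**Table shells.** Tables 2.1.1, 2.1.2, 2.2.1 and 2.2.2 each have a row for the median duration of disease control, and footnote 4 gives it an exact binomial interval. The two bracketed figures are also called a range in the row label of Table 2.1.1 and in footnote 4 of Tables 2.1.2 and 2.2.1. Table 2.2.2 mentions only the binomial interval. None of the four has a disease control rate row.

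**The concern.** The plan uses one name for two quantities and gives the first the confidence interval of the second. A programmer who follows SAP 7.4.5 literally cannot produce a valid interval for the duration. Nor does the section say what to do with a subject whose disease is still controlled at data cut-off, so two programmers could report different medians from the same data. The one quantity that the exact binomial method suits, the rate, has no planned output that shows it with an interval.

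The stakes are confined to a reported secondary result. SAP 3.3 calls all analyses exploratory, and the Simon rule counts only CR and PR.

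**Working it through.** **1. Compare the three time-to-event efficacy endpoints in the SAP.**

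| | PFS (7.4.8) | DOR (7.4.4) | Duration of disease control (7.4.5) |
|---|---|---|---|
| Endpoint type | time | time | time |
| Estimator | Kaplan-Meier | Kaplan-Meier | not stated; shells show a median without a method |
| 95% CI | Brookmeyer-Crowley | Brookmeyer-Crowley | exact binomial |
| Censoring | Table 5 | as for PFS | not stated |

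For DOR the link is explicit: "Censoring of DOR will follow the same algorithm as the censoring of PFS". Section 7.4.5 has no such sentence. It imports only the progression criteria of 7.4.2.2, which is the mRECIST v1.1 section. Protocol 9.4.1.2 also names Kaplan-Meier for PFS and DOR alone.

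**2. What the named interval produces.** For x of n subjects the exact (Clopper-Pearson) 95% limits are the 2.5% point of Beta(x, n − x + 1) and the 97.5% point of Beta(x + 1, n − x). For an illustrative 9 controlled of the 17 evaluable subjects in a full cohort, they are 27.8% and 77.0%. These are percentages of subjects. They suit a rate and have no meaning beside a median time.

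**3. A charitable reading.** A distribution-free interval for a median can be built from Binomial(n, 0.5): ranks 2 and 8 of 9 ordered times give 96.1% coverage, and ranks 5 and 13 of 17 give 95.1%. The SAP does not describe this interval, which needs uncensored times. The rate denominator that follows in 7.4.5 also points to a proportion.

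**4. What an unstated censoring rule could do.** The documents give neither a median nor a censoring share, so the following are assumptions: exponential durations, true median 24 weeks, 20%, 30% or 40% censored, and censored times counted as events. The reported median is then the median of min(duration, censoring time). Under exponential censoring it equals 24 × (1 − censored share): 24 × 0.8 = 19.2, 24 × 0.7 = 16.8, 24 × 0.6 = 14.4. The other two rows come from 2,000,000 simulated durations.

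| Censoring pattern | 20% | 30% | 40% |
|---|---|---|---|
| Exponential | 19.2 | 16.8 | 14.4 |
| Uniform | 19.8 | 17.9 | 16.0 |
| Same fixed follow-up for all | 24.0 | 24.0 | 24.0 |

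Fixed follow-up shows no bias because the cut-offs needed (55.7, 41.7 and 31.7 weeks) all lie beyond the true median. The shortfall runs from 0% to (24 − 14.4)/24 = 40%.

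A second simulation, with 9 subjects and a true median of 4 months, agrees. At 10%, 30% and 50% exponential censoring the naive median is about 3.6, 2.8 and 2.0 months, while the typical Kaplan-Meier median stays at about 4.0.

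**5. What a valid interval would look like.** For 9 controlled subjects, a 24-week median and 30% exponential censoring (20,000 simulated cohorts), typical Brookmeyer-Crowley limits on the linear scale are about 10 and 55 weeks, with no upper limit in 17% of cohorts. On the log-log scale they are about 2.7 and 61.6 weeks, with no upper limit in 20%. The SAP does not name a scale.

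**6. Outputs.** SAP 7.4.5 promises swim plots for this endpoint under both criteria. The figure list (4.1.1 to 4.1.5) has a swim plot for DOR only.

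**The case against.** The best defense concedes the mismatched interval and argues that the rest is small.

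- **Shells are guidance.** Appendix A lets the shells and lists be changed without an SAP amendment if the nature of the analysis is unaffected. That largely answers the missing rate row, the range label and the missing swim plot, so these are minor. It does not reach the body text of 7.4.5, and choosing between a proportion and a time does change the nature of the analysis.
- **The rate is recoverable.** Protocol 9.4.1.2 supplies a numerator (CR + PR + SD), SAP 7.4.5 a denominator rule and a suitable interval, and the shells show CR, PR and SD counts that can be summed. This is fair for the point estimate. But the numerator is labeled a duration, which is the confusion itself, and no row shows the rate or its interval.
- **Analysts would copy DOR.** That is plausible, since the terminating events are the same and Table 5 is in the same document. But the SAP wrote that link for DOR, omitted it here, and prescribed a different interval.
- **The size is assumed.** This stands. No passage proposes counting censored times as events, and the range includes no bias. The Brookmeyer-Crowley limits depend on the scale and show the imprecision of 9 subjects, not harm from the wording.
- **No Kaplan-Meier figure was promised.** Correct, so its absence is not an inconsistency.
- **The 49-day SD minimum is a separate question.** Section 7.4.2.1 states it for RECIST v1.1 only. The description of mRECIST v1.1 as an adaptation suggests that it carries over. It is worth one sentence because it decides who counts as controlled.

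**Conclusion.** The concern holds. SAP 7.4.5 defines a time and gives it an interval for a proportion, footnote 4 repeats this in four shells, and Protocol 9.4.1.2 contradicts Protocol 2.2.2 on what the endpoint is. These are faults of text and need no assumption. The missing estimator and censoring rule are equally plain beside 7.4.4 and 7.4.8.

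Only the numerical effect is uncertain. Under the assumptions in the working, the median could be reported as anything from correct to 40% too short. This should be corrected before programming, but it does not threaten the trial's main conclusions: the Simon stopping rule, the promising/nonpromising decision and the sample size do not use disease control.

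**What to change.** Split the endpoint in SAP 7.4.5:

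1. **Disease control rate:** the proportion with best overall response of CR, PR or SD, using the denominator rule already in 7.4.5, with an exact binomial 95% CI. State whether the 49-day SD minimum also applies under mRECIST v1.1.
2. **Duration of disease control:** among subjects with disease control, the Kaplan-Meier median with a Brookmeyer-Crowley 95% CI, censored by Table 5 as for DOR, with progression under mRECIST v1.1 taken from 7.4.2.2.

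Then name the rate in SAP 2.3.2 and 7.1, correct the definition in Protocol 9.4.1.2, align footnote 4 and the row labels in Tables 2.1.1, 2.1.2, 2.2.1 and 2.2.2, add a rate row to each, and add the promised swim plot to the figure list.

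The cost is wording in four sections, one row and one footnote in each of four shells, and one figure entry. No new data are needed, and both methods are already in the SAP.

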## 7.4.6. Largest Percentage Reduction in Sum of Diameters of Target Lesions

For each subject in the FAS population with target lesions at baseline, target lesion sizes will be measured by sum of diameters. The best percentage change from baseline, defined as the largest decrease in target lesion size for each subject, will be summarized descriptively, and a waterfall plot of the best percentage change will be generated.

Per RECIST criteria, target lesions considered "too small to measure" will be assigned a default value of 5 mm for purposes of this analysis. Likewise, target lesions identified as "not present" at postbaseline assessments will be assigned 0 mm for this analysis. In the event a target lesion is unaccounted for in a particular postbaseline timepoint (ie, assessment missing or NE), then the overall sum of diameters for target lesions will not be evaluable for that postbaseline timepoint.

## 7.4.7. Percentage Change in Sum of Diameters of Target Lesions Over Time

For each subject in the FAS population with target lesions at baseline, target lesion sizes will be measured by sum of diameters. The percentage change in sum of diameter of target lesions over time will be listed and a spider plot will be generated.

## 7.4.8. Progression-Free Survival

Progression-free survival is defined as the length of time between the baseline visit (Day 1) and the earlier of death or PD as assessed by RECIST v1.1 and mRECIST v1.1. Date of death will be determined using the Death Report CRF.

Censoring for PFS will follow the algorithm outlined in Table 5, which is based on the FDA Guidance for Industry: Clinical Trial Endpoints for the Approval of Cancer Drugs and Biologics (FDA 2007).

Kaplan-Meier curves for PFS will be presented by cohort-specific tumor types. The KM estimate of median PFS will be presented with its 95% CI. The 95% CI will be calculated using the Brookmeyer and Crowley's method (Brookmeyer and Crowley 1982).

Table 5: Evaluation and Censoring of Progression-Free Survival

| Situation   | Outcome    | Date of Progression or Censoring   |
|---|------------|--|
| No baseline tumor assessments                                 | Censored   | Date of Day 1  |
| No valid postbaseline response assessments                    | Censored   | Date of Day 1  |
| Progression documented between scheduled response assessments | Progressed | Date of first overall response of PD   |
| No progression  | Censored   | Date of last valid radiologic assessment (not NE and not missing)  |
| Study discontinuation for undocumented progression            | Censored   | Date of last valid radiologic assessment (not NE and not missing)  |
| Study discontinuation for toxicity or other reason            | Censored   | Date of last valid radiologic assessment (not NE and not missing)  |
| New anticancer treatment started                              | Censored   | Date of last valid radiologic assessment (not NE and not missing) on/before starting a new anticancer treatment. (Date of PD assessment if the new anticancer treatment started after PD.) |
| Death before first progressive response assessment            | Progressed | Date of death  |
| Death between adequate response assessments                   | Progressed | Date of death  |
| Death or progression after more than 1 missed assessments     | Censored   | Date of last valid radiologic assessment (not NE and not missing) before death   |

NE = not evaluable.

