## 7.4.2.2. Objective Response Rate by mRECIST v1.1

The mRECIST v1.1 instrument was adapted from RECIST v1.1 to include criteria that accounts for new lesions that can occur in immuno-oncology subjects before the occurrence of an SD, PR, or CR. Under mRECIST v1.1, if radiologic imaging shows PD, tumor assessment should be repeated at a minimum of 4 weeks but not more than 6 weeks later to confirm the progression. If there is no second PD tumor assessment in the 4- to 6-week follow-up time, the PD will be defined as unconfirmed. Table 4 lists the scenarios that can occur after an unconfirmed PD in at least 4 weeks and no more than 6 weeks and provides rules for determining whether or not the unconfirmed PD will be counted as an event in the corresponding scenario.

Table 4: Rules for Determining PD Event Status After an Unconfirmed PD

| Event Occurring After Unconfirmed PD in the Confirmation Window (4-6 weeks) | PD Event Status   |
|---|---|
| Subject had EOS/EOT or started new anticancer therapy.                      | PD will be confirmed as a PD.   |
| Subject had a confirmed PD.   | PD will be confirmed as a PD.   |
| Subject had an CR, PR, SD, or NE.   | PD will not be considered as a PD and counted as corresponding CR, PR, SD, or NE for the second timepoint only. |

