### 7.4.4.1. Duration of Response by RECIST v1.1

Under RECIST v1.1, for objective responders, DOR is defined as the time from the first overall response contributing to an objective response (CR or PR) to the earlier of the subject's death from any cause or first assessment of PD.

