#### 7.4.8.1. Progression-Free Survival by RECIST v1.1

Under RECIST v1.1, PFS is defined as the length of time between the baseline visit (Day 1) and the earlier of death or first assessment of PD as assessed by RECIST v1.1.

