### 7.4.8.2. Progression-Free Survival by mRECIST v1.1

Under mRECIST v1.1, PFS is defined as the length of time between the baseline visit (Day 1) and the earlier of death or first overall confirmed assessment of PD (as described in Section 7.4.2.2).

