### 7.4.8.2.1. Confirmation of Progression per mRECIST v1.1

Under mRECIST v1.1, the assessment of PD will be confirmed by a second consecutive assessment at least 4 weeks but no later than 6 weeks apart with the option for continuing treatment while awaiting radiologic confirmation of progression (Table 4).

• If after the first unconfirmed PD, there is an EOT/EOS or a new treatment is started, this unconfirmed PD will be counted as a confirmed PD, and DOR will be defined as the time from the first overall response (CR or PR) to this PD, or death from any cause if occurring sooner than the PD.

- If a second PD occurs after the first unconfirmed PD, the first unconfirmed PD will be counted as a confirmed PD, and DOR will be defined as the time from the first overall response (CR or PR) to the first PD, or death from any cause if occurring sooner than the confirmed PD.
- If a CR, PR, SD, or NE occurs after the first unconfirmed PD, the unconfirmed PD will not be counted as a PD. If there is no further PD assessment, DOR will be censored.

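### SAP Table 5 labels progression followed by new anticancer therapy as censored, contradicting the plan's own PFS and DOR event definitions

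*SAP*

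**What the plan says.** SAP Section 7.4.8 makes Table 5 the operative censoring algorithm for PFS. The row for new anticancer treatment has a single entry in the outcome column, Censored. Its date cell covers two situations. Ordinarily the date is the last valid scan up to the start of the new therapy. A parenthesis then adds: "Date of PD assessment if the new anticancer treatment started after PD".

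The other relevant text is as follows.

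- Table 5, documented progression: "Progression documented between scheduled response assessments | Progressed | Date of first overall response of PD".
- Section 7.4.8.1: RECIST v1.1 PFS ends at "the earlier of death or first assessment of PD as assessed by RECIST v1.1".
- Section 7.4.8.2: mRECIST v1.1 PFS ends at "the earlier of death or first overall confirmed assessment of PD".
- Section 7.4.4.1: RECIST v1.1 DOR ends at "death from any cause or first assessment of PD".
- Section 7.4.2.2, Table 4: among the events that turn an unconfirmed PD into a confirmed one is "Subject had EOS/EOT or started new anticancer therapy". Section 7.4.8.2.1 says of that case that "this unconfirmed PD will be counted as a confirmed PD".
- Section 7.4.4: "Censoring of DOR will follow the same algorithm as the censoring of PFS".

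Table 5 does not say which row governs when a subject meets more than one.

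**The concern.** A subject whose scan shows PD and who later receives another therapy fits two rows of Table 5. One makes the subject an event at the PD date and the other makes the same subject censored at the PD date. The date is the same in both, so only the event flag differs, and an error in that flag is hard to see in a listing.

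The consequence runs in one direction. Changing an event to a censored time on the same day can never lower a Kaplan-Meier curve, so any relabelled event leaves the PFS or DOR estimate unchanged or higher. The censoring is also informative, because it falls at the moment of failure. Part 2 cohorts are planned at no more than 17 evaluable subjects (Protocol Section 4.1.3), and DOR is estimated in responders only, so a few wrong flags can shift a median or leave it unreached.

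**Working it through.** **No stated figure to reproduce.** The plan gives no event count, precision or power for PFS or DOR. The check is therefore a comparison of the rules, followed by a sensitivity range.

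**Step 1: apply each rule to one subject (PD on a scan, then new therapy).**

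| Source | Status at the PD date |
|---|---|
| Table 5, new-treatment row | Censored |
| Table 5, documented-progression row | Event |
| Sections 7.4.8.1 and 7.4.4.1 (RECIST v1.1) | Event |
| Section 7.4.8.2 with Table 4 and Section 7.4.8.2.1 (mRECIST v1.1) | Event |

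One row of Table 5 disagrees with everything else.

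**Step 2: do the definitions settle it?** Not by themselves. The last row of Table 5 censors a death or progression that follows more than one missed assessment. There the table deliberately overrides the event definition. A programmer cannot tell from the text whether the new-treatment row is a second deliberate override or a labelling slip. Under mRECIST v1.1, Table 4 and Section 7.4.8.2.1 deal with this exact sequence and largely settle it as an event. RECIST v1.1 has no such specific text.

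**Step 3: size under the literal reading.** Let d be the share of PFS events that are deaths without PD, and f the share of progressors who start new therapy and have it recorded. Both are assumptions; the documents give neither.

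Share of PFS events lost: L = (1 − d) × f. More than half are lost when f exceeds 0.5 / (1 − d).

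| d | f = 20% | f = 50% | f = 80% | f above which most events are lost |
|---|---|---|---|---|
| 0% | 20% | 50% | 80% | 50% |
| 10% | 18% | 45% | 72% | 56% |
| 20% | 16% | 40% | 64% | 63% |
| 30% | 14% | 35% | 56% | 71% |

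**Step 4: effect on a median.** With a constant hazard, and relabelling unrelated to event time, the event rate is multiplied by (1 − L) and the median by 1 / (1 − L): 1.25 at L = 20%, 2.0 at L = 50% and 3.3 at L = 70%. A simulation of a small cohort agrees in direction and rough size. It used 17 subjects, 15 true events, exponential times and 4,000 runs per setting. The typical Kaplan-Meier median with no events lost was 1.15 time units.

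| L | Mean events left | Typical median | Ratio to 1.15 | Median not reached |
|---|---|---|---|---|
| 20% | 12.0 | 1.43 | 1.2 | 0% of runs |
| 50% | 7.5 | 2.25 | 2.0 | 7% of runs |
| 70% | 4.5 | 4.05 | 3.5 | 35% of runs |

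These figures are for PFS. DOR follows the same formula with its own d and f, but no separate figure can be supported.

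**Step 5: with the row corrected.** If PD followed by new therapy is an event, L = 0 from this row for every d and f.

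**The case against.** The best defence is that the parenthesis was meant to describe an event. It sits in a column that holds either a progression date or a censoring date, and it replaces the row's usual censoring date with the PD date, which is where an event would be placed. The same subject also meets the row marked Progressed, and every definition of PFS and DOR agrees. On that reading no event is lost. This is probably the intention, but the outcome cell says otherwise, and Step 2 shows why the definitions cannot be presumed to win. The defence explains the slip without removing it.

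Three limits on the point do stand.

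- The analyses are declared exploratory (SAP Section 3.3). PFS and DOR are secondary and described by Kaplan-Meier estimates with 95% intervals, with no test. The Simon decisions use response counts.
- The rate of later therapy is undocumented. Eligible subjects have progressed on, cannot tolerate or refuse available treatment (Protocol Section 3.1), which does not establish that further therapy is usual. Protocol Table 7 schedules collection of post-study therapy only at the 30- and 60-day safety visits, which may lower f.
- Table 4 makes mRECIST v1.1 much less exposed than RECIST v1.1.

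A reader might also infer that PD seen at a scheduled scan has no event row, because the documented-progression row speaks only of progression between scheduled assessments. That strains a row title: the date rule in the row has no such limit, and the reading would contradict the PFS definitions. Retitling is editorial.

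**Conclusion.** The outcome label in the new-treatment row of Table 5 is wrong for therapy begun after PD, or at best contradicts the rest of the SAP. Without a precedence rule it can be programmed literally, and DOR inherits it. If that happens, true events are removed and PFS and DOR are biased upward, mainly under RECIST v1.1.

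The loss would be 14-20% of PFS events if 20% of progressors have recorded new therapy, 35-50% at half, and 56-80% at 80%. Each range assumes that 0 to 30% of PFS events are deaths without PD.

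It is tempting to conclude that most PFS and DOR events would disappear. The documents do not support that. It needs the literal label to prevail over every event definition and a recorded new-therapy share above about 50 to 71%, which the plan never states. Objective response rate, the Simon stopping rules and the primary safety endpoint are untouched. This is a definite error to correct before PFS and DOR are programmed, with consequences confined to descriptive secondary endpoints.

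**What to change.** Replace the single row in Table 5 with two:

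- (a) New anticancer treatment before documented PD: Censored, at the last valid assessment on or before its start.
- (b) New anticancer treatment after documented PD: Progressed, at the date of first PD (for mRECIST v1.1, as determined by Table 4), subject to the existing missed-assessment row.

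Add a sentence giving the order of precedence among the rows and confirming that it applies to DOR through Section 7.4.4. For clarity, retitle the PD row *Progression documented at or between scheduled assessments*.

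The cost is SAP wording only. Data collection, sample size and design do not change.
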